6.9.1. Rescue Medicine

There is no rescue therapy to reverse the AEs observed with PF-07284890; standard medical supportive care must be provided to manage the AEs.

7. DISCONTINUATION OF STUDY INTERVENTION AND PARTICIPANT DISCONTINUATION/WITHDRAWAL

7.1. Discontinuation of Study Intervention

It may be necessary for a participant to permanently discontinue study intervention. Reasons for permanent discontinuation of study intervention include the following:

- AE requiring discontinuation in investigator's view;
- Positive COVID-19 test.

If study intervention is permanently discontinued, the participant will not remain in the study for further evaluation. See the [SoA](#) for data to be collected at the time of discontinuation of study intervention.

7.1.1. ECG Changes

A participant who meets either bulleted criterion based on ECG readings will be withdrawn from the study intervention.

- QTcF >500 ms.
- Change from baseline: QTcF >60 ms and QTcF >450 ms.

If a clinically significant finding is identified (including, but not limited to, changes from baseline in QTcF after enrollment), the investigator or qualified designee will determine if the participant can continue in the study and if any change in participant management is needed. This review of the ECG printed at the time of collection must be documented. Any new clinically relevant finding should be reported as an AE.

7.1.2. Potential Cases of Acute Kidney Injury

Abnormal values in SCr concurrent with presence or absence of increase in BUN that meet the criteria below, in the absence of other causes of kidney injury, are considered potential cases of acute kidney injury and should be considered important medical events.

An increase of ≥ 0.3 mg/dL (or ≥ 26.5 μ mol/L) in SCr level relative to the participant's own baseline measurement should trigger another assessment of SCr as soon as practically feasible, preferably within 48 hours from awareness.

If the second assessment (after the first observations of ≥ 0.3 mg/dL [or ≥ 26.5 μ mol/L] in SCr relative to the participant's own baseline measurement) is ≥ 0.4 mg/dL (or ≥ 35.4 μ mol/L), the participant should be discontinued from the study and adequate, immediate, supportive measures taken to correct apparent acute kidney injury.

Participants should return to the investigator site and be evaluated as soon as possible, preferably within 48 hours from awareness of the second assessment confirming abnormal SCr result. This evaluation should include laboratory tests, detailed history, and physical assessment. In addition to repeating SCr, laboratory tests should include serum BUN, serum creatine kinase, and serum electrolytes (including at a minimum potassium, sodium, phosphate/phosphorus, and calcium), in addition to urinary dipstick, urine microscopic examination, and urinary indices. All cases confirmed on repeat testing as meeting the laboratory criteria for acute kidney injury, with no other cause(s) of laboratory abnormalities identified, should be considered potential cases of drug-induced kidney injury irrespective of availability of all the results of the investigations performed to determine etiology of the abnormal SCr. If ≥ 2 healthy participants in a given period are noted to have 2 *consecutive* SCr results of ≥ 0.3 mg/dL (or ≥ 26.5 μ mol/L), an assessment of whether the finding may be considered an adverse drug reaction should be undertaken.

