- a. Screening will be performed within 28 days prior to the first dose of PF-07284890.
- b. Period 2 will begin on Study Period 1, Day 5 (referred to as Period 2, Day -1). Period 3 will begin on Study Period 2, Day 5 (referred to as Period 3, Day -1). Day -1 activities will be performed only for Day -1 of Period 1 unless otherwise indicated.
- c. Participants will be admitted to the CRU at least 12 hours prior to PF-07284890 dose on Day 1 of Period 1. Participants will be discharged on Day 4 of Study Period 3 following completion of all assessments.
- d. Medical history will include a history of prior illegal drug, alcohol, and tobacco use, as well as blood donation within prior 60 days. Medical history will be recorded at screening and updated on Day -1 of Period 1.
- e. Demographics will include participant race, ethnicity, age, and gender during the screening visit.
- f. Physical examination will be performed by trained medical personnel at the investigator site at screening or Day -1 of Period 1 only (height and weight must be obtained at screening to obtain BMI for eligibility criteria). A brief PE will be performed on Day -1 of Periods 2 and 3, and may be performed at other designated time points at the discretion of the investigator.
- g. Safety laboratory assessments including urinalysis, hematology, chemistry and coagulation will be performed at the indicated time-points, including Day -1 and Day 2 at 24 hours post-dose of all 3 Periods. All the safety laboratory samples must be collected following at least a 4-hour fast. Additional safety laboratory assessments may be performed at any time at the discretion of the investigator.
- h. For postmenopausal (amenorrheic for at least 12 consecutive months) female participants only.
- i. Urine drug and cotinine (mandatory) and alcohol breath test (at discretion of the investigator) will be performed at screening from Days -28 to -2 and again on Day -1 of Period 1. These tests may be performed at any other time at the discretion of the investigator.
- j. The investigator or his/her designee will discuss with the participant the need to use highly effective contraception consistently and correctly according to contraception guidelines.

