4. STUDY DESIGN

4.1. Overall Design

This is a Phase 1, open-label, randomized, single dose, 3-treatment, 2-sequence, 3-period crossover study to evaluate the effect of a low-fat and high-fat meal on the relative bioavailability of PF-07284890 following a single oral dose of PF-07284890 using two 100-mg tablets of PF-07284890 in healthy adult participants, males and females of non-childbearing potential. The study will consist of 3 treatments: a single oral dose of 200 mg PF-07284890 (2 × 100 mg tablets) under fasted conditions (Treatment A, Reference), a single oral dose of 200 mg PF-07284890 (2 × 100 mg tablets) under low-fat meal fed conditions (Treatment B, Test 1), and a single oral dose of 200 mg PF-07284890 (2 × 100 mg tablets) under high-fat meal fed conditions (Treatment C, Test 2). There will be a total of 2 treatment sequences shown in Section 1.2 with the assigned Treatments A, B or C in each treatment period.

Approximately 12 healthy participants will be randomly assigned to study intervention such that approximately 6 participants will be enrolled to each sequence. Participants who discontinue from the study for non-safety reasons may be replaced at the sponsor's discretion in collaboration with the investigator.

Healthy participants will be screened to determine eligibility within 28 days prior to study treatment. Medical history and results of physical examination, physical measurements, vital signs, 12-lead ECGs, and clinical laboratory evaluations will determine eligibility.

Each enrolled participant will participate in 3 study periods to receive 3 different treatments according to the sequence determined by randomization with 5-day washouts between PF-07284890 administration:

- Treatment A: Single oral dose of 200 mg PF-07284890 (2 × 100 mg tablets) under fasted conditions (Reference).
- Treatment B: Single oral dose of 200 mg PF-07284890 (2 × 100 mg tablets) under fed conditions, low-fat meal (Test 1).
- Treatment C: Single oral dose of 200 mg PF-07284890 (2 × 100 mg tablets) under fed conditions, high-fat meal (Test 2).

Participants will be randomly assigned to 1 of 2 sequences as shown in Section 1.2. Serial PK samples will be collected at timepoints shown in the [SoA](#).

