10.7. Appendix 7: Kidney Safety: Monitoring Guidelines

10.7.1. Laboratory Assessment of Change in Kidney Function and Detection of Kidney Injury

Standard kidney safety monitoring requires assessment of baseline and postbaseline serum creatinine (Scr measurement to estimate glomerular filtration rate [Scr-based eGFR] or creatinine clearance [eCrCl]). Baseline and postbaseline serum Scys makes it feasible to distinguish AKI from other causes of Scr increase. If Scr increase is confirmed after baseline, then reflex measurement of Scys is indicated to estimate the combined Scr-Scys eGFR calculation (for adults only).

Regardless of whether kidney function monitoring tests are required as a routine safety monitoring procedure in the study, if the investigator or sponsor deems it necessary to further assess kidney safety and quantify kidney function, then these test results should be managed and followed per standard of care.

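### Protocol 7.1.2 omits the change-from-baseline qualifier from the 0.4 mg/dL discontinuation rule and the 0.3 mg/dL group-review rule, so ordinary creatinine values satisfy both numbers as written

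*Protocol*

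**What the plan says.** Protocol 7.1.2 (Potential Cases of Acute Kidney Injury) sets three serum creatinine (SCr) thresholds.

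- **Repeat trigger.** An increase of at least 0.3 mg/dL (26.5 µmol/L) "in SCr level relative to the participant's own baseline measurement should trigger another assessment of SCr".
- **Discontinuation.** The sentence opens "If the second assessment (after the first observations of ≥ 0.3 mg/dL" and continues, after the unit conversion, to "relative to the participant's own baseline measurement) is ≥ 0.4 mg/dL" (35.4 µmol/L). If this is met, the participant should be discontinued from the study.
- **Group review.** If two or more participants in a period have two consecutive "SCr results of ≥ 0.3 mg/dL" (26.5 µmol/L), the possibility of an adverse drug reaction is to be assessed.

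Protocol Appendix 7 (10.7.1) adds: "If Scr increase is confirmed after baseline, then reflex measurement of Scys is indicated". It gives no numerical threshold. Protocol 8.3.5 only points to that appendix. SAP 3.5.2 defines each period's laboratory baseline as the Day -1 measurement but does not restate the kidney rules.

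Safety laboratory draws are scheduled in each period, "including Day -1 and Day 2 at 24 hours post-dose of all 3 Periods" (Schedule of Activities, footnote g). On replacement, Protocol 4.1 says: "Participants who discontinue from the study for non-safety reasons may be replaced".

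**The concern.** Only the first threshold is written as a change from baseline. In the discontinuation sentence the baseline phrase sits inside the parenthesis recalling the first observation, so what must reach 0.4 mg/dL is the second assessment itself. The group-review sentence has no reference to an increase at all.

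The repeat sample is there to separate a confirmed rise from a transient one. If a normal repeat value meets the threshold, the rule no longer does that. Likewise, a group trigger that healthy participants meet routinely cannot act as a signal.

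Site staff apply these rules directly. Discontinuation is permanent (Protocol 7.2), and the high-fat treatment is always in Period 3. A needless stop in Period 1 or 2 loses that participant's high-fat data. A stop in Period 1 also loses the fasted versus low-fat pair. The study plans on 12 evaluable participants, and the replacement provision names only non-safety discontinuations.

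**Working it through.** There is no plan figure to reproduce. The check compares the wording of the three rules, then asks how ordinary the values 0.3 and 0.4 mg/dL are.

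**1. The three rules side by side**

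| Rule in 7.1.2 | Quantity compared, as written | Baseline attached to this threshold? | Consequence |
|---|---|---|---|
| Repeat trigger, 0.3 mg/dL | Increase in SCr | Yes | Repeat SCr |
| Discontinuation, 0.4 mg/dL | The second assessment | No, only to the first observation | Discontinue from study |
| Group review, 0.3 mg/dL | Two consecutive results | No | Assess as possible adverse drug reaction |

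The unit pairs agree with each other: 26.5/0.3 = 88.3 and 35.4/0.4 = 88.5 µmol/L per mg/dL. The numbers are therefore not misprints. Only the qualifier is missing.

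**2. Worked example (assumed values)**

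Baseline 0.9, first post-dose value 1.2, repeat 0.9 mg/dL.

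- First value: 1.2 − 0.9 = 0.3, so a repeat is due under either reading.
- Repeat, as written: 0.9 ≥ 0.4, so discontinue.
- Repeat, as a change: 0.9 − 0.9 = 0.0 < 0.4, so continue.

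More generally, if the repeat is back at baseline, the literal rule spares the participant only when baseline is below 0.4 mg/dL. With the qualifier restored, the cut-offs for assumed baselines of 0.6 to 1.1 mg/dL are 1.0 to 1.5 mg/dL for discontinuation (baseline + 0.4) and 0.9 to 1.4 mg/dL for group review (baseline + 0.3).

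**3. What 0.4 mg/dL means under the protocol's own 2021 CKD-EPI equations (10.7.2.1)**

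- Men: eGFR = 142 × (0.4/0.9)^−0.302 × 0.9938^age = 162 at age 18 and 121 at age 65.
- Women: eGFR = 143 × (0.4/0.7)^−0.241 × 0.9938^age = 146 at age 18 and 109 at age 65.

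The eligibility floor of 75 mL/min/1.73 m² (Protocol 5.2, criterion 12) corresponds to SCr of about 1.40 (age 18) to 1.09 (age 65) in men and 1.09 to 0.86 in women. An eligible participant can therefore sit well above both 0.3 and 0.4 mg/dL with normal kidney function.

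**4. Share of values meeting each number (assumed normal SCr)**

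The documents give no SCr distribution, so mean and SD are assumptions. Share at or above x = 1 − Φ((x − mean)/SD).

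| Mean, SD (mg/dL) | At least 0.4 | At least 0.3 |
|---|---|---|
| 0.6, 0.10 | 97.7% | 99.9% |
| 0.6, 0.18 (least favourable) | 86.7% | 95.2% |
| 0.8, 0.15 | 99.6% | 99.96% |
| 1.0, 0.18 | 99.96% | 99.99% |

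A lognormal with mean 0.6 and SD 0.18 gives 89.2% and 98.7%. So if the repeat has returned to baseline, the literal 0.4 rule spares between under 0.1% (1 − 0.9996) and about 13% (1 − 0.8667) of the unconfirmed rises.

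**5. Group review, least favourable case**

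With two independent results per participant, p = 0.9522² = 0.907. Among 12 participants, P(at least 2) = 1 − 0.093^12 − 12 × 0.907 × 0.093^11 > 0.9999. Positive correlation between a person's two results would raise p.

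**The case against.** The strongest reply is that context settles the meaning.

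- Section 7.1.2 opens by speaking of abnormal creatinine, describes the stop as a response to apparent kidney injury, and treats the second assessment as confirming an abnormal result. A repeat back at baseline confirms nothing.
- The 0.4 rule is reached only after a first rise of at least 0.3 mg/dL over baseline, so an ordinary creatinine value alone stops nobody.
- Protocol 8.1 requires safety issues to be discussed with the sponsor to decide whether the participant continues.
- Under SAP 3.5.2, Day -1 is the period's baseline. If it is not counted as a result, the scheduled draws supply only one result per period towards the group rule.
- The percentages above show that normal creatinine exceeds 0.3 to 0.4 mg/dL. They do not say how often a transient rise of 0.3 mg/dL will occur.

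Most of this stands as a limit on impact. The prior-rise condition is real, a careful physician would probably read the rule as intended, and the number of needless stops cannot be estimated from the documents. The Day -1 point narrows how the group rule is reached, but the sentence itself does not exclude that draw, and any repeat or unscheduled result would meet the wording just as easily. None of it makes the written thresholds correct. The contextual phrases carry no number, and a stopping rule should not depend on staff correcting it as they apply it.

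**Conclusion.** The concern holds as a wording error in an operative safety rule. The discontinuation and group-review thresholds in Protocol 7.1.2 are written as absolute creatinine values, where change from baseline is evidently meant.

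Its importance is small. The literal error over-discontinues and over-reviews but misses no injury. The group rule leads only to an assessment. The primary analysis method is unaffected, and the study is exposed only through possible needless loss of participants.

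The defect itself rests on the text alone. The shares of values meeting each threshold rest on the assumed mean of 0.6 to 1.0 mg/dL and SD of 0.10 to 0.18 mg/dL.

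**What to change.** Amend two sentences of Protocol 7.1.2 and leave the numbers as they are:

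- **Discontinuation:** require that the second assessment shows an increase of ≥ 0.4 mg/dL (≥ 35.4 µmol/L) over the participant's own baseline.
- **Group review:** require two consecutive results that each show an increase of ≥ 0.3 mg/dL (≥ 26.5 µmol/L) over the participant's own baseline.

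The cost is a few words. Visits, sampling and analysis do not change.

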7.1.3. COVID-19

If a participant has COVID-19 during the study, this should be reported as an AE or SAE (as appropriate) and appropriate medical intervention provided. Temporary discontinuation of

the study intervention may be medically appropriate until the participant has recovered from COVID-19. It is recommended that the investigator discuss temporary or permanent discontinuation of study intervention with the study medical monitor.

It is recommended that the investigator discuss temporary or permanent discontinuation of study intervention with the study medical monitor.

7.2. Participant Discontinuation/Withdrawal From the Study

A participant may withdraw from the study at any time at their own request. Reasons for discontinuation from the study include the following:

- Refused further study procedures;
- Lost to follow-up;
- Death;
- Study terminated by sponsor;
- Investigator's decision;

At the time of discontinuing from the study, if possible, an early discontinuation visit should be conducted. See the [SoA](#) for assessments to be collected at the time of study discontinuation and follow-up and for any further evaluations that need to be completed.

The early discontinuation visit applies only to participants who are enrolled/randomized and then are prematurely withdrawn from the study. Participants should be questioned regarding their reason for withdrawal.

The participant will be permanently discontinued from the study intervention and the study at that time.

If a participant withdraws from the study, they may request destruction of any remaining samples taken and not tested, and the investigator must document any such requests in the site study records and notify the sponsor accordingly.

If the participant withdraws from the study and also withdraws consent (see Section 7.2.1) for disclosure of future information, no further evaluations will be performed and no additional data will be collected. The sponsor may retain and continue to use any data collected before such withdrawal of consent.

7.2.1. Withdrawal of Consent

Participants who request to discontinue receipt of study intervention will remain in the study and must continue to be followed for protocol-specified follow-up procedures. The only exception to this is when a participant specifically withdraws consent for any further contact with them or persons previously authorized by the participant to provide this information.

Participants should notify the investigator in writing of the decision to withdraw consent from future follow-up, whenever possible. The withdrawal of consent should be explained in detail in the medical records by the investigator, as to whether the withdrawal is only from further receipt of study intervention or also from study procedures and/or posttreatment study follow-up, and entered on the appropriate CRF page. In the event that vital status (whether the participant is alive or dead) is being measured, publicly available information should be used to determine vital status only as appropriately directed in accordance with local law.

7.3. Lost to Follow-up

A participant will be considered lost to follow-up if the participant repeatedly fails to return for scheduled visits and is unable to be contacted by the study site.

The following actions must be taken if a participant fails to attend a required study visit:

- The site must attempt to contact the participant and reschedule the missed visit as soon as possible. Counsel the participant on the importance of maintaining the assigned visit schedule and ascertain whether the participant wishes to and/or should continue in the study;
- Before a participant is deemed lost to follow-up, the investigator or designee must make every effort to regain contact with the participant (where possible, 3 telephone calls and, if necessary, a certified letter to the participant's last known mailing address or local equivalent methods). These contact attempts should be documented in the participant's medical record;
- Should the participant continue to be unreachable, the participant will be considered to have withdrawn from the study.

8. STUDY ASSESSMENTS AND PROCEDURES

8.1. Administrative Procedures

The investigator (or an appropriate delegate at the investigator site) must obtain a signed and dated ICD before performing any study-specific procedures.

Study procedures and their timing are summarized in the [SoA](#). Protocol waivers or exemptions are not allowed.

Safety issues should be discussed with the sponsor immediately upon occurrence or awareness to determine whether the participant should continue or discontinue study intervention.

Adherence to the study design requirements, including those specified in the [SoA](#), is essential and required for study conduct.

All screening evaluations must be completed and reviewed to confirm that potential participants meet all eligibility criteria. The investigator will maintain a screening log to

record details of all participants screened and to confirm eligibility or record reasons for screening failure, as applicable.

Participants will be screened within 28 days prior to administration of the study intervention to confirm that they meet the study population criteria for the study. If the time between screening and dosing exceeds 28 days as a result of unexpected delays (eg, delayed drug shipment), then participants do not require rescreening if the laboratory results obtained prior to first dose administration meet eligibility criteria.

Every effort should be made to ensure that protocol-required tests and procedures are completed as described. However, it is anticipated that from time to time there may be circumstances outside the control of the investigator that make it unfeasible to perform the test. In these cases, the investigator must take all steps necessary to ensure the safety and well-being of the participant. When a protocol-required test cannot be performed, the investigator will document the reason for the missed test and any corrective and preventive actions that they have taken to ensure that required processes are adhered to as soon as possible. The study team must be informed of these incidents in a timely manner.

If an IV catheter is utilized for blood sample collections, ECGs and vital sign assessments (pulse rate and BP) should be collected prior to the insertion of the catheter.

For samples being collected and shipped, detailed collection, processing, storage, and shipment instructions and contact information will be provided to the investigator site prior to initiation of the study.

The total blood sampling volume for individual participants in this study is approximately 210 mL. The actual collection times of blood sampling may change. Additional blood samples may be taken for safety assessments at times specified by Pfizer, provided the total volume taken during the study does not exceed 550 mL during any period of 56 consecutive days.

To prepare for study participation, participants will be instructed on the information in the [Lifestyle Considerations](#) and [Concomitant Therapy](#) sections of the protocol.

